3.3.5 Replacement of patients

Patients may be replaced for determination of the primary endpoint (MTD) in cases of:

- Patient's withdrawal during the first cycle of treatment for reasons other than DLT, e.g. patient no longer wishes to participate, or lost to follow up during first cycle.
- Patients who do not experience DLT, but miss more than one dose of xentuzumab during the first cycle of treatment, except for dose interruption caused by AE
- Patients who do not experience DLT, but miss 3 or more consecutive doses of abemaciclib during the first cycle of treatment, except for dose interruption caused by AE.
- Patients who miss one complete cycle at any time beyond the first cycle of treatment may be replaced after discussion between the sponsor and the investigator.
- Patients who are non-evaluable with respect to DLT.
- Patients with CTCAE grade ≥ 3 allergic reaction/hypersensitivity to the study drug(s) within the first cycle may be replaced.
- For cohorts E and F, where objective response or DC is the primary endpoint: if patient doesn't have post-treatment radiological tumor assessment for reason other than worsening of underlying disease

Patients that have been replaced might continue treatment in the trial should criteria in [Section 4.1.4.2](#) apply; however these patients will not be considered for analysis of the primary endpoint.

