4.4.2 Management and grading of infusion reactions

The xentuzumab infusion should always be administered under close supervision of a medically qualified staff member with immediate availability of appropriate resuscitation facilities.

Infusion reactions may occur during infusion with xentuzumab and include pyrexia, chills, rigors, dyspnoea, urticaria, bronchospasm, hypotension and hypertension. **A one hour observation period is recommended following each infusion.** If there is no infusion reaction during the first treatment course, the observation period following xentuzumab infusion may be adjusted at the discretion of the investigators. Mild to moderate infusion reactions may be managed with a slower infusion rate and prophylactic antihistamines for subsequent dosing. Severe reactions require immediate and permanent discontinuation of infusion. The hypersensitivity reactions will be graded according to the National Cancer Institute (NCI) Common Terminology Criteria for Adverse Events (CTCAE) version 4.03 ([R10-4848](#)).

The infusion duration may be extended to over one hour and up to a maximum of three hours.

The infusion reactions should be treated symptomatically as judged clinically relevant by the investigator. For symptomatic treatment of infusion reactions: hydrocortisone, antihistamines such as chlorphenamine accompanied by an antipyretic/analgesic and/or a bronchodilator is recommended.

Infusion reactions will not be reported on the standard AE page but will be reported on a separate page specifically for infusion reactions in the CRF.

Table 4.4.2: 1 Infusion reaction management

Infusion Reaction Grade	Management
CTCAE Grade 1 or 2	In the event of a CTCAE grade 1 infusion reaction, the infusion rate should be reduced by 50%. A Grade 2 infusion reaction may require symptomatic treatment, as described above (with infusion interruption). Once the event has resolved, the infusion may be restarted at the reduced rate.
CTCAE Grade 3	For patients experiencing a CTCAE grade 3 infusion reaction, infusion should be interrupted immediately and patients should receive aggressive symptomatic treatment, as described above. Only after all the symptoms have disappeared, the infusion may be re-started if it is within 3 hours since the infusion start. The infusion rate should be reduced by half after re-start

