5.3.7 Dose Limiting Toxicities (DLTs)

A dose limiting toxicity (DLT) in this study is defined as an adverse event or laboratory abnormality which 1) is considered related, probably related or possibly related to study drug and 2) meets any of the following criteria, unless that toxicity can be clearly attributed to cancer progression or to another clearly identified etiology:

- CTCAE Grade 3 hyperglycaemia lasting > 48 hours
- CTCAE Grade 4 hyperglycaemia
- CTCAE Grade ≥ 3 pneumonitis
- CTCAE Grade ≥ 3 febrile neutropenia
- CTCAE Grade 4 hematologic toxicity lasting longer than 5 days
- CTCAE Grade 4 thrombocytopenia of any duration and Grade 3 thrombocytopenia associated with bleeding
- AST or ALT $> 5x$ ULN (for baseline AST/ALT \leq ULN) or $>$ (baseline value + 4x ULN) (for baseline AST/ALT $>$ ULN)
- CTCAE Grade ≥ 3 diarrhoea, nausea, or vomiting lasting more than 2 days despite maximal supportive care
- CTCAE Grade ≥ 3 skin rash despite adequate supportive care measures
- CTCAE Grade ≥ 3 fatigue/asthenia lasting for more than seven days
- Grades 3 to 4 hyperlipidaemia (total cholesterol > 400 mg/dL or triglycerides > 500 mg/dL) not improving despite appropriate treatment for 2 weeks

Proprietary confidential information © 2024 Boehringer Ingelheim International GmbH or one or more of its affiliated companies

- Any AE necessitating a 2-week treatment interruption (except for hematologic AEs)
- All other non-hematologic toxicities of CTCAE Grade ≥ 3 (except alopecia, infusion-related reaction and those mentioned above)
- Any other study drug related toxicity considered significant enough to be qualified as DLT in the opinion of the investigators, and confirmed by the safety review with the BI clinical monitor and BI project physician (TMM), will be reported as a DLT

For the purposes of dose finding, only DLT events that occur during the first treatment period of 28 days will be considered. Decisions regarding dose escalation/de-escalation steps will be made only after discussion between the sponsor and the investigators, and in consideration of all the available safety information. Available data of DLTs occurring after first treatment course and all unusual/unexpected AE at any time during treatment will be considered for the purpose of recommending the dose for cohorts B, C, D (dose finding), E, F, D1 and D2.

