7.3.1 Primary endpoint analyses

For dose finding cohorts A, B, C, and D (dose finding):

In order to identify the MTD, the number of patients with DLTs during the MTD evaluation period at each dose level will be presented. Patients who discontinue during the first treatment course for reasons other than DLT will be excluded from the determination of MTD.

For expansion cohort E:

Objective response will be analysed in terms of objective response rate, defined as the proportion of patients with best overall response of CR or PR (note that no confirmation is required for best overall response).

For cohorts D1 and D2:

PFS rate at 18th month will be derived using Kaplan Meier method. Cohort D1 for visceral vs. cohort D2 for non-visceral will be displayed separately. The details will be described in the TSAP.

For expansion cohort F

DC will be analysed in terms of DC rate, defined as the proportion of patients with best overall response of CR, PR, SD lasting for at least 24 weeks or non-CR/non-PD lasting for at least 24 weeks.

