6.3 PATIENTS SETS ANALYSED

The following analysis sets will be defined for this trial:

- Enrolled set (ENR)

This patient set includes all patients with informed consent given. The enrolled set will be used for patient disposition tables.

- Treated set (TS)

This patient set includes all patients who are documented to have received and taken at least one dose of any study medication during the treatment cycles (including run-in period).

The TS will be used for all planned safety and efficacy analyses.

- MTD Set (MS)

The MTD set defines the set of patients in the dose-finding cohorts (cohorts A,B,C and D) of the trial that are fully evaluable for determination of the MTD in the first treatment course. The MTD set will be used for some safety analyses for dose-finding cohorts, this is specified in the technical TSAP.

[figure not shown]
Patients in the TS who were replaced within the MTD period in the dose-finding cohorts (cohorts A,B,C and D) of the trial will be excluded from the determination of the MTD. Patients in the TS who entered in an expansion cohorts will be also excluded from the determination of the MTD. Replacement of patients in the dose-finding cohorts of the study is defined in Section 3.3.5 of the CTP. The final list of replaced patients is supplied by the Clinical Trial Leader (CTL) no later than the last report planning meeting before the database lock for the safety analysis.

- Pharmacokinetic set (PKS)

Proprietary confidential information © 2021 Boehringer Ingelheim International GmbH or one or more of its affiliated companies

This patient set includes all patients in the treated set who have at least one valid drug plasma concentration available. The decision whether a concentration is considered valid or not will in general be made at the RPM before Database Lock (DBL) or URPM and documented within the respective meeting minutes. Values to be excluded from analyses identified during analysis would be documented within the respective QC forms. The PKS will be used for the PK analyses of the trial.

No per protocol population will be used for analyses.

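### The hypersensitivity replacement bullet in Protocol 3.3.5 has no DLT limit, so a patient with a cycle-1 DLT can be left out of the MTD estimate

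*Protocol*

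**What the plan says.** Protocol 3.3.5 introduces its list with "Patients may be replaced for determination of the primary endpoint (MTD) in cases of". One bullet reads: "Patients with CTCAE grade ≥ 3 allergic reaction/hypersensitivity to the study drug(s) within the first cycle may be replaced". The section ends by letting replaced patients stay on treatment; "however these patients will not be considered for analysis of the primary endpoint".

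Other bullets in the list protect DLTs. The withdrawal bullet covers only reasons other than DLT. Both cycle-1 missed-dose bullets are limited in the same way; the xentuzumab one begins "Patients who do not experience DLT, but miss more than one dose of xentuzumab during the first cycle of treatment".

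The DLT definition in Protocol 5.3.7 requires an event to be at least possibly related to study drug. Its catch-all criterion is "All other non-hematologic toxicities of CTCAE Grade ≥ 3 (except alopecia, infusion-related reaction and those mentioned above". Infusion-related reaction is exempt; allergic reaction and hypersensitivity are not named as exempt.

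Protocol 7.3.1 states: "Patients who discontinue during the first treatment course for reasons other than DLT will be excluded from the determination of MTD".

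SAP 6.3 removes from the MTD determination "Patients in the TS who were replaced within the MTD period in the dose-finding cohorts". SAP 7.4.1 repeats this, and leaves replacement to a case-by-case decision that the trial team confirms before database lock.

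**The concern.** The MTD is the highest combination with less than a 25% risk that the true DLT rate exceeds 33%. That estimate needs every evaluable patient with a DLT in the count. The hypersensitivity bullet is triggered by a toxicity, and nothing in it asks whether that toxicity, or another one in the same patient, met the DLT definition. Where it did, the patient can be taken out of the estimate because of the outcome, by an optional decision in an open-label trial, after the outcome is known. That biases the estimated DLT rate downward. The numbers per dose are small (3 to 6, about 12 per cohort), so a single event can decide whether a combination satisfies overdose control. The dose chosen in cohort D also carries forward to cohorts F, D1 and D2.

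**Working it through.** **Step 1: which patients are affected.** Take a patient with a cycle-1 Grade ≥3 reaction and read 3.3.5 against 5.3.7.

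- Infusion-related reaction, no other DLT: exempt under 5.3.7. Replacement removes no DLT.
- Infusion-related reaction plus another event meeting 5.3.7: the bullet still applies, and the other DLT leaves with the patient.
- Drug-related hypersensitivity that is not an infusion reaction (for example to oral abemaciclib or a hormonal agent): a DLT under the catch-all. Replacement removes it.
- A xentuzumab reaction that could carry either label: unclear. Protocol 4.4.2, on infusion reactions, says "The hypersensitivity reactions will be graded according to the National Cancer Institute (NCI) Common Terminology Criteria for Adverse Events (CTCAE) version 4.03", and SAP Table 7.8.1:1 builds its infusion-reaction category from the hypersensitivity MedDRA query. Neither document says where the exemption ends.

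**Step 2: the model.** Inputs are Protocol 7.1 and Table 7.1:3. At 150 mg abemaciclib with 1000 mg xentuzumab both doses equal their reference doses, so the slope terms vanish:

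- π1 = 1/(1+exp(−log α1)), π2 = 1/(1+exp(−log α2))
- π0 = π1 + π2 − π1·π2
- odds(π) = π0/(1−π0) · exp(η)

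Priors:

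- log α1: 0.9·N(−3.697, SD 1.031) + 0.1·N(−4, SD 2)
- log α2: 0.9·N(−2.515, SD 0.829) + 0.1·N(−3, SD 2)
- η: N(0, SD 0.707)

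For r DLTs in n patients each prior draw has weight w = π^r·(1−π)^(n−r), and P(OD) = Σ w·1[π ≥ 0.33] / Σ w. The calculation used 4,000,000 draws.

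**Step 3: reproduce the plan.** P(OD) at 150/1000, data written as DLTs/patients:

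| Data | Plan (Tables 7.1:4, 10.6:1) | Rebuilt |
|---|---|---|
| prior | 0.098 | 0.099 |
| 0/3 | 0.027 | 0.026 |
| 1/3 | 0.141 | 0.145 |
| 2/3 | 0.430 | 0.426 |
| 0/6 | 0.009 | 0.008 |
| 1/6 | 0.048 | 0.050 |

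The largest difference is 0.004.

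**Step 4: remove one DLT patient and add a DLT-free replacement.** The overdose-control limit is 0.25.

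| Observed | P(OD) | After replacement | P(OD) | Decision |
|---|---|---|---|---|
| 2/3 | 0.426, fails | 1/3 | 0.145, passes | reversed |
| 3/6 | 0.427, fails | 2/6 | 0.183, passes | reversed |
| 1/3 | 0.145, passes | 0/3 | 0.026, passes | same |
| 2/6 | 0.183, passes | 1/6 | 0.050, passes | same |

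The crude rate moves from 2/3 = 67% to 1/3 = 33%, and from 3/6 = 50% to 2/6 = 33%. The plan's own Table 10.6:1 shows the first reversal: 0.430 with a move to a lower combination, against 0.141 and staying. In the second, the six remaining patients also meet the second MTD criterion of Protocol 7.1.

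**Step 5: is it the removal or the extra patient?** Keep the DLT patient and simply add the DLT-free one: 2/4 gives 0.323 and 3/7 gives 0.343. Both still fail, so the removal causes the reversal.

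**The case against.** Four points on the other side carry weight.

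1. A reader might infer that 5.3.7 makes every Grade ≥3 hypersensitivity a DLT. It does not. Infusion-related reactions are exempt, and the documents treat xentuzumab infusion reactions largely as hypersensitivity. Many patients caught by the bullet may therefore have had no DLT. This stands, and it narrows the point to the second and third groups in Step 1, plus the unclear fourth.

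2. A reader might infer that replacement can only lower the DLT count. That assumes a DLT-free replacement. If the replacement also has a DLT, 2/3 stays 2/3; if the replaced patient had only an exempt reaction, the count can rise. What remains is narrower: discarding a patient because of a DLT biases the estimated rate downward.

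3. A reader might infer a flat contradiction with 7.3.1. That section does not say its exclusions are exhaustive, and 3.3.5 lists others, such as missed doses. It is a tension, arising when the option is used for a patient whose reaction was a DLT.

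4. There are other safeguards. The Steering Committee sees non-DLT adverse events and later-cycle data (4.1.2.1). All DLTs are tabulated (7.3.4), and safety analyses use the treated set (SAP 7.8). The event is therefore not hidden. But 4.1.2.1 requires any declared MTD1/RP2D1 to satisfy overdose control, and that calculation would run without the event. The later model re-run in Protocol 5.1.1 does not say that replaced patients return.

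On frequency, Protocol 2.3 reports three serious infusion reactions, one of them Grade 3 or higher, and 1.2 gives about 494 treated patients. Those are of the exempt type, so they do not size the problem.

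**Conclusion.** The bullet is wrong as written, within limits. As it stands, a patient with a cycle-1 DLT can be left out of the MTD estimate because of a severe hypersensitivity reaction, where that reaction is itself a DLT or accompanies another one. One such removal can reverse the overdose-control decision at 150/1000: P(OD) 0.43 to 0.14 for three patients, 0.43 to 0.18 for six. This assumes the cohort A prior, all data at that combination and a DLT-free replacement. From 1/3 or 2/6 it changes no decision. The documents give no frequency for the relevant reactions, so the expected bias cannot be computed.

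They also do not support saying that the plan as a whole estimates the DLT rate only among patients free of severe hypersensitivity: replacement is optional and decided patient by patient. SAP 3 says safety analyses were performed after each dose-finding cohort, so escalation cannot now be changed; what is open is the final MTD set.

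**What to change.** - Reconcile Protocol 3.3.5, 5.3.7 and 7.3.1 with SAP 6.3 and 7.4.1. The sponsor should state whether, and when, a hypersensitivity reaction falls under the infusion-reaction exemption.
- Limit the hypersensitivity bullet in 3.3.5 to patients without a DLT, as the missed-dose bullets already are.
- State in SAP 6.3 and 7.4.1 that a patient with any cycle-1 event meeting 5.3.7 stays in the MTD set, whether or not another patient was added.
- As dose finding is complete, report whether any patient with a DLT was replaced under this bullet. If so, re-run the final model with that patient included and show both results.

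The cost is a few sentences and, at most, a repeat of an existing analysis. The downside is that the DLT rate may come out slightly less favourable.

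### Replacement for Grade ≥3 hypersensitivity in cycle 1 has no DLT exception, so a protocol-defined DLT that is not an infusion reaction can drop out of the MTD calculation

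*Protocol*

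**What the plan says.** **Replacement (Protocol 3.3.5).** The cycle-1 withdrawal rule is limited to reasons other than DLT. The missed-dose rules carry a similar condition, for example "Patients who do not experience DLT, but miss more than one dose of xentuzumab during the first cycle of treatment". The hypersensitivity rule does not: patients with Grade ≥3 "allergic reaction/hypersensitivity to the study drug(s) within the first cycle may be replaced". Replaced patients may stay on treatment, "however these patients will not be considered for analysis of the primary endpoint".

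**DLT definition (Protocol 5.3.7).** Any other non-hematologic toxicity of Grade ≥3 that is at least possibly related to study drug is a DLT, "except alopecia, infusion-related reaction and those mentioned above". Hypersensitivity that is not an infusion reaction is not on that list of exceptions.

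**Primary analysis (Protocol 7.3.1).** "Patients who discontinue during the first treatment course for reasons other than DLT will be excluded from the determination of MTD".

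**SAP.** Section 6.3 says that patients replaced within the MTD period in the dose-finding cohorts "of the trial will be excluded from the determination of the MTD", with no exception for a DLT. Section 7.4.1 excludes patients replaced under Protocol 3.3.5, case by case, with confirmation by the trial team before database lock. Section 7.8 limits exclusion to replacement within or before the first cycle.

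**How the count is used.** Under Protocol 7.1 a dose is admissible only if the posterior probability of a DLT rate of 0.33 or more is below 0.25. Under 4.1.2.1 any MTD or RP2D that the Steering Committee declares must meet that limit. The committee also reviews adverse events that are not DLTs and events after cycle 1.

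**The concern.** A patient's DLT status should decide whether the patient counts in the MTD analysis. Here a discretionary replacement can override it. Take a patient with a related Grade ≥3 allergic reaction to an oral study drug in cycle 1. Section 5.3.7 makes the event a DLT. If the patient stops because of it, 7.3.1 gives no ground for exclusion. Yet 3.3.5 permits replacement, and the SAP then takes the patient out of the MTD set.

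The removal works in one direction: a DLT leaves the numerator and a new patient takes the place. The trial is open-label and the exclusion is confirmed after the outcome is known. At stake is whether a dose that fails the overdose limit on the full data can pass it on the reduced data.

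**Working it through.** **1. Inputs.** The model and limit come from Protocol 7.1, the priors from Table 7.1:3, and the reference results from Tables 7.1:4 and 10.6:1. Doses are written abemaciclib/xentuzumab.

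- Single agents, k = 1 (xentuzumab), 2 (abemaciclib): logit(π_k) = log(α_k) + β_k·log(d_k/d_k*), with d_1* = 1000 mg and d_2* = 150 mg.
- No interaction: π⁰ = π_1 + π_2 − π_1·π_2.
- With interaction: odds(π) = odds(π⁰)·exp(η·(d_1/d_1*)·(d_2/d_2*)), where η has mean 0 and SD 0.707.
- Main prior components (weight 0.9) for (log α, log β): xentuzumab means −3.697, −0.517, SDs 1.031, 0.816, correlation 0.034; abemaciclib means −2.515, 0.898, SDs 0.829, 0.808, correlation −0.510. The weight-0.1 components are as in the same table.
- Posterior: 4 million prior draws, each weighted by π^r·(1−π)^(n−r) for r DLTs in n patients. P(OD) is the weight with π ≥ 0.33.

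**2. Reproducing the plan's figures.** Prior P(OD) at 150/1000 is 0.099 (stated 0.098). For Table 10.6:1, P(OD) at the current dose is:

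| Scenario | Computed | Stated |
|---|---|---|
| 1 (0/3) | 0.026 | 0.027 |
| 2 (1/3) | 0.145 | 0.141 |
| 3 (2/3) | 0.426 | 0.430 |
| 4 (0/6) | 0.008 | 0.009 |
| 5 (1/6) | 0.050 | 0.048 |
| 6 | 0.053 | 0.053 |
| 7 | 0.081 | 0.081 |

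All seven recommended next doses match, and every difference is within 0.005.

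**3. Effect of replacement at 150/1000.** The like-for-like contrast enrols the extra patient (without a DLT) in both arms. The only difference is whether the patient with the hypersensitivity DLT is counted.

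| Other DLTs | Kept | P(OD) | Dropped | P(OD) | Limit 0.25 |
|---|---|---|---|---|---|
| 1 | 2/4 | 0.323 | 1/3 | 0.145 (stated 0.141) | fails, then passes |
| 2 | 3/7 | 0.343 | 2/6 | 0.183 | fails, then passes |
| 1 | 2/7 | 0.137 | 1/6 | 0.050 | passes both |
| 0 | 1/7 | 0.035 | 0/6 | 0.008 | passes both |

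In the first row the recommendation moves from 150/750 to 150/1000. In the second row 150/1000 becomes admissible, but its target-interval probability ties with that of 150/750 at 0.473, so only the admissibility result is firm. In the last two rows the recommendation is 150/1000 either way. In a group of three, a lone DLT also changes nothing: Table 10.6:1 gives 0.141 for 1/3 and 0.027 for 0/3, both passing. A further DLT is thus necessary for an effect, but not sufficient.

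**4. How likely (assumption).** The documents give no rate for Grade ≥3 hypersensitivity that is not an infusion reaction. Assume 1% to 5%, with other DLTs at 15% (the prior mean of 0.150 at 150/1000 in Table 7.1:4) and the two kinds mutually exclusive within a patient. Exactly one of each among three patients has probability 6·p·q·(1−p−q):

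- 6 × 0.15 × 0.01 × 0.84 = 0.0076, about 0.8%
- 6 × 0.15 × 0.05 × 0.80 = 0.036, or 3.6%

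**The case against.** **Most such events may not be DLTs.** Protocol 4.4.2 speaks of hypersensitivity reactions when it grades infusion reactions, and SAP Table 7.8.1:1 finds infusion-related reactions with a hypersensitivity query. For an event classed as an infusion reaction, 3.3.5 and 5.3.7 agree and no DLT is lost. A history of hypersensitivity to the study drugs is also an exclusion criterion. This stands and narrows the point. It does not close it, because 3.3.5 covers every study drug, including oral ones, and the overlap in terms means that the label alone can decide whether an event counts.

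**Replacement is optional and the event stays visible.** This also stands. A reader might infer that the toxicity disappears from the dose decision. The documents do not support that: the Steering Committee sees it under 4.1.2.1, and Protocol 7.3.4 tabulates DLTs by dose level. What it can leave is the model input, and the overdose limit on a declared dose is computed from that input.

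**The missed-cycle rule.** A reader might infer the same flaw from "Patients who miss one complete cycle at any time beyond the first cycle of treatment may be replaced". The SAP does not bear that out. Sections 6.3 and 7.8 confine exclusion to replacement in the MTD period or within or before cycle 1, and by then the DLT has already entered the model. Only the closing sentence of 3.3.5 and the cross-reference in SAP 7.4.1 point the other way. This is a mismatch between the protocol and the SAP.

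**Timing.** SAP section 3 reports the dose-finding safety analyses as done, so an edit cannot change past dose decisions. It still bears on the final MTD analysis and on the model re-run after expansion that Protocol 5.1.1 foresees.

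**Conclusion.** The conflict is real but narrow. It concerns related Grade ≥3 hypersensitivity in cycle 1 that is not an infusion reaction, in a patient whom the team chooses to replace. For that patient, following the stated rules can remove a protocol-defined DLT from the overdose calculation.

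The size is P(OD) of about 0.32 against about 0.14 at 150/1000, on either side of the 0.25 limit, when one other DLT is present in a small group. A reader might take 0.430 against 0.141 straight from Table 10.6:1. That overstates the effect, because it ignores that the extra patient could be enrolled without dropping the first.

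The DLT counts are illustrative, and the 0.8% to 3.6% likelihood rests wholly on assumed rates. The documents do not say whether anyone was replaced under this rule. A correction is worthwhile because the rule is wrong as written and cheap to repair, not because a wrong dose is shown to have been chosen.

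**What to change.** 1. Reconcile Protocol 3.3.5, 5.3.7 and 7.3.1 with SAP 6.3 and 7.4.1, so that the DLT definition and the exclusions from the MTD set agree. How hypersensitivity is classified clinically is for the sponsor to decide. Once that is settled, state that no event counting as a DLT under the reconciled definition can be removed from the MTD set by replacement.
2. Align the closing sentence of 3.3.5 and SAP 7.4.1 with SAP 6.3, so that replacement for a cycle missed after cycle 1 does not remove a patient already evaluable for DLT.
3. In the final MTD analysis, list any patient replaced under these two rules and re-run the model with that patient included.

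The cost is about one clause in each document and a short listing. A model re-run is needed only if such a patient exists.

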7.3 PLANNED ANALYSES

No per protocol set will be used in the analysis. However, important protocol violations will be summarised. The TSAP will specify the important protocol violations in detail.

For the determination of the MTD, only MTD evaluable patients will be considered. For the analysis of primary and secondary endpoints of the expansion parts and further endpoints of dose finding and expansion parts, all patients in the treated set (i.e. patients treated with at least one dose of any trial medication, including hormonal therapy) will be included in the analysis. Any other analysis sets will be defined in the TSAP.

The analysis of the primary endpoint of the dose finding cohorts (cohorts A, B, C and D (dose finding) respectively) will be conducted when “last-patient-last-visit-primary-endpoint-dose-finding” has been reached (see [Section 8.6](#)).

Primary analysis of expansion cohorts (cohort E, F, D1 and D2) might be done before the end of the study. The further details will be described in TSAP.

The results of each dose finding cohorts (A, B, C, and D (dose finding)) and each expansion cohorts (E, F, D1 and D2) will be analysed separately.

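### Protocol 3.3.5 drops replaced cohort E and F patients from the primary endpoint, contradicting protocol 7.3 and the SAP, which analyse all treated patients

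*Protocol*

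**What the plan says.** Protocol 3.3.5 lists the grounds for replacing a patient. Most concern DLT evaluability in the first cycle, but one is specific to two expansion cohorts: "For cohorts E and F, where objective response or DC is the primary endpoint", a patient may be replaced "if patient doesn't have post-treatment radiological tumor assessment for reason other than worsening of underlying disease". The section closes with a sentence about all replaced patients. They may continue treatment, "however these patients will not be considered for analysis of the primary endpoint".

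Protocol 7.3 restricts the evaluable-only rule to MTD determination. For the expansion cohorts' primary and secondary endpoints, its rule is that "all patients in the treated set (i.e. patients treated with at least one dose of any trial medication, including hormonal therapy) will be included".

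The SAP follows 7.3:
- SAP 6.3: "The TS will be used for all planned safety and efficacy analyses". The exclusion of replaced patients there is from MTD determination only and covers "Patients in the TS who were replaced within the MTD period in the dose-finding cohorts" A to D. SAP 7.8 repeats this.
- SAP 6.2: nobody is excluded from the analyses except for missing consent or breach of the age limit.
- SAP 5.1.2: a patient without a post-baseline image is classed as not evaluable (NE), in a subcategory for a missing post-baseline image.
- SAP 7: the patient set in use defines the denominator.
- SAP 7.4.2 and 7.4.4: the cohort E and F results show the number of treated patients with counts and percentages.
- SAP 4.2: changes from the protocol are marked as not applicable.

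**The concern.** A treated cohort E or F patient who stops for toxicity or withdraws before the first scan is handled in two ways. Under 3.3.5 the patient can be replaced and leaves the primary analysis. Under 7.3 and the SAP the patient stays in the denominator.

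The 3.3.5 rule selects on what happened after treatment began. It removes people who did not stay long enough to be scanned, and none of them can be a success. In a single-arm cohort of about 20 patients with no comparator, the observed rate is the whole result, so a few exclusions can move it visibly. Because the protocol carries both rules, a report on either denominator could cite it in support.

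**Working it through.** **1. The plan's own figures.** Protocol 7.7 treats cohorts E and F as binomial with n = 20.
- P(X ≥ 10 | n = 20, p = 0.60) = 0.8725. The plan states 87%.
- P(X ≥ 8 | n = 20, p = 0.20) = 0.0321. The plan states 3%.

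Both reproduce. They do not settle the denominator: the synopsis and section 3.1 call the 20 patients evaluable, while 7.7 says 20 patients will be treated. With no replacements the two descriptions coincide.

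**2. The rules side by side, for a treated E or F patient with no scan who is replaced.**

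| Source | In the primary denominator? |
|---|---|
| Protocol 3.3.5, closing sentence | No |
| Protocol 7.3 | Yes |
| SAP 6.2, 6.3, 7, 7.4.2, 7.4.4 | Yes |
| SAP 5.1.2 | Classed as NE, so not a success |

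**3. Direction.** Let x be the successes among 20 evaluable patients and k the number replaced under the no-scan ground. I read post-treatment scan as a scan after treatment has started. A patient without one cannot have CR, PR or stable disease lasting to week 24, so the k patients add nothing to the numerator.

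- Rate under 3.3.5: x / 20
- Rate on the treated set: x / (20 + k)
- Difference: x/20 − x/(20 + k) = xk / [20(20 + k)]

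The difference is never negative. It is zero only when x = 0 or k = 0.

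**4. Size, as an illustration.** The documents do not give k, so assume 1 to 4. Assume also x = 12, which gives 12/20 = 60.0% under 3.3.5.

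| k | Treated-set rate | Difference from 60.0% |
|---|---|---|
| 1 | 12/21 = 57.1% | 2.9 points |
| 2 | 12/22 = 54.5% | 5.5 points |
| 3 | 12/23 = 52.2% | 7.8 points |
| 4 | 12/24 = 50.0% | 10.0 points |

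**The case against.** The strongest reply is that the analysis sections already settle the denominator. Protocol 7.3 names the treated set for the expansion cohorts' primary endpoints. SAP version 2.0 (25 October 2021) postdates the amendments that put cohorts E and F into 3.3.5 (Amendment 3 of December 2018, revised for F in Amendment 7 of July 2020). It cites 3.3.5 by number and still confines the exclusion of replaced patients to MTD. On that view only one sentence is out of line. This largely stands: a programmer following the SAP would keep these patients in. It does not remove the contradiction, because the sentence is still in the protocol revision of 4 March 2022, which is later than the SAP.

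A second reply is that 3.3.5 opens by tying replacement to MTD as the primary endpoint, so its last sentence may concern MTD alone. That fails. The E and F ground names objective response or disease control as the primary endpoint, those cohorts determine no MTD, and the closing sentence is unqualified.

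In the other direction, a reader might infer that the planned primary rates are biased upward, or that both denominators are equally in force. The documents do not support that: upward bias arises only if 3.3.5 is applied over 7.3 and the SAP and at least one patient is replaced. A reader might also take 60% as a pass mark that 57.1% would miss. Protocol 7.7 gives 60% as an assumed true rate that would be clinically relevant. Its worked probabilities use at least 10 and at least 8 events out of 20, and protocol 7.2 plans no formal test.

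**Conclusion.** The contradiction is real and lies mainly inside the protocol, between 3.3.5 and 7.3. The SAP sides with 7.3 without recording a departure from 3.3.5. The likely reported denominator is the treated set, so this is a correction to the protocol text rather than evidence of a biased analysis.

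If 3.3.5 were applied, the cohort E response rate or cohort F disease-control rate would be higher or unchanged, never lower. The illustrative gap is 2.9 to 10.0 points for 1 to 4 replaced patients. That range rests on the assumed 12 successes in 20 and the assumed number replaced, and it vanishes if nobody is replaced. The direction is certain only for the no-scan ground; a patient replaced on another ground might have been scanned. No error rate or decision rule in the plan is affected.

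**What to change.** In protocol 3.3.5, limit the closing sentence to MTD determination in cohorts A to D, as SAP 6.3 already does. Add that replaced cohort E and F patients remain in the treated-set denominator, counted as non-responders (E) or without disease control (F), using the existing SAP category NE with missing post-baseline image.

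A rate among evaluable patients only is optional as a supportive figure. If it is wanted, SAP 6.3 needs a definition of that set, since it lists none.

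The cost is one or two sentences. No new data, sample-size change or change to patient management is needed. The downside is that the reported rate may be lower than 3.3.5 would have given, by the 2.9 to 10.0 points shown under the illustrative assumptions.
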